Annex Table 1-5 (cont'd) Other comorbidity

Disease description	ICD-10 code	ICPC code
Malignancy	C00-C97	A79 Malignancy NOS B72 Hodgkin's disease/lymphoma B73 Leukaemia B74 Malignant neoplasm blood other D74 Malignant neoplasm stomach D75 Malignant neoplasm colon/rectum D76 Malignant neoplasm pancreas D77 Malig. neoplasm digest other/NOS F74 Neoplasm of eye/adnexa H75 Neoplasm of ear K72 Neoplasm cardiovascular N74 Malignant neoplasm nervous system R84 Malignant neoplasm bronchus/lung R85 Malignant neoplasm respiratory, other S77 Malignant neoplasm of skin T71 Malignant neoplasm thyroid U75 Malignant neoplasm of kidney U76 Malignant neoplasm of bladder
Malignancy (cont'd)		U77 Malignant neoplasm urinary other W72 Malignant neoplasm relate to preg. X75 Malignant neoplasm cervix X76 Malignant neoplasm breast female X77 Malignant neoplasm genital other (f) Y77 Malignant neoplasm prostate Y78 Malign neoplasm male genital other
Depressive disorders	F32-F33	P76 Depressive disorder
Pregnancy (at the index date)	O00-O48	W78 Pregnancy W79 Unwanted pregnancy

ICD-10 = *International Statistical Classification of Diseases and Related Health Problems, 10th Revision*;
ICPC = *International Classification of Primary Care*.

Proprietary confidential information © 2017 Boehringer Ingelheim International GmbH or one or more of its affiliated companies

Annex Table 1-6 Anatomical Therapeutic Chemical codes for comedications

Medication description	ATC code
Respiratory medications	
Inhaled SAMAs	
Ipratropium bromide	R03BB01
Oxitropium bromide	R03BB02
Inhaled LAMAs	
Tiotropium bromide	R03BB04
Aclidinium bromide	R03BB05
Glycopyrronium bromide	R03BB06
Inhaled SABAs	
Salbutamol	R03AC02
Terbutaline	R03AC03
Fenoterol	R03AC04
Rimiterol	R03AC05
Hexoprenaline	R03AC06
Isoetarine	R03AC07
Pirbuterol	R03AC08
Tretoquinol	R03AC09
Carbuterol	R03AC10
Tulobuterol	R03AC11
Clenbuterol	R03AC14
Reproterol	R03AC15
Procaterol	R03AC16
Bitolterol	R03AC17
Indacaterol	R03AC18
Inhaled LABAs	
Salmeterol	R03AC12
Formoterol	R03AC13

Proprietary confidential information © 2017 Boehringer Ingelheim International GmbH or one or more of its affiliated companies

Annex Table 1-6 (cont'd) Anatomical Therapeutic Chemical codes for comedICATIONS

Medication description	ATC code
Respiratory medications (cont'd)	
Inhaled LABA/ICS	
Salmeterol and fluticasone	R03AK06
Formoterol and budesonide	R03AK07
Formoterol and beclometasone	R03AK08
Formoterol and mometasone	R03AK09
Vilanterol and fluticasone furoate	R03AK10
Formoterol and fluticasone	R03AK11
Salmeterol and budesonide	R03AK12
Inhaled glucocorticosteroid	
Beclometasone	R03BA01
Budesonide	R03BA02
Flunisolide	R03BA03
Betamethasone	R03BA04
Fluticasone	R03BA05
Triamcinolone	R03BA06
Mometasone	R03BA07
Ciclesonide	R03BA08
Fixed combinations of SABAs and SAMAs	ATC codes not available ¹
Fixed combinations of SABAs and ICSs	ATC codes not available ¹
Fixed combinations of LABAs and ICSs	ATC codes not available ¹
Systemic glucocorticosteroids	H02AB
Systemic beta2-agonists	R03CC
Xanthines and fixed dose combinations of xanthines with adrenergics	R03DA, R03DB
Roflumilast	R03DX07
Nasal glucocorticosteroids	R01AD
Omalizumab	R03DX05
Leukotriene receptor antagonists	R03DC
Cromoglicic acid	R03BC01
Nedocromil	R03BC03

Proprietary confidential information © 2017 Boehringer Ingelheim International GmbH or one or more of its affiliated companies

Annex Table 1-6 (cont'd) Anatomical Therapeutic Chemical codes for comedICATIONS

Medication description	ATC code
Respiratory medications (cont'd)	
Oxygen therapy	V03AN01
Nebuliser therapy	ATC codes not available ¹
Cardiovascular medications	All codes listed below in section Cardiovascular medications
Cardiac glycosides and antiarrhythmics, Classes I and III	C01A, C01B
Vasodilators used in cardiac diseases	C01D
Other cardiac preparations	C01B, C01C
Diuretics	C03
Peripheral vasodilators	C04
Beta blocking agents	C07
Calcium channel blockers	C08
Antihypertensives	C02
Agents acting on the renin-angiotensin system	C09
Angiotensin-converting-enzyme inhibitors	C09A, C09B
Angiotensin II receptor antagonists	C09C, C09D
Renin-inhibitors	C09X
Lipid-modifying agents	C10
HMG CoA reductase inhibitors (statins)	C10AA
Other lipid-modifying agents	C10AB, C10AC, C10AD, C10AX
HMG CoA reductase inhibitors (statins), other combination	C10BX
Antithrombotic agents	B01
Platelet aggregation inhibitors	B01AC
Systemic antibacterials	J01
Iron preparations	B03A
Proton pump inhibitors	A02BC
Drugs used in diabetes	A10

Proprietary confidential information © 2017 Boehringer Ingelheim International GmbH or one or more of its affiliated companies

Annex Table 1-6 (cont'd) Anatomical Therapeutic Chemical codes for comedications

Medication description	ATC code
Drugs for musculoskeletal system	M01A, N02BA, M01B, M01C
Antidepressants	N06A
Antineoplastic agents	L01
Immunosuppressants	L04
Antivirals for systemic use	J05
Hormone-replacement therapy: Estrogens, progestogens, and estrogens in combination	G03C, G03D, G03F
Drugs used in nicotine dependence	N07BA

ATC = Anatomical Therapeutic Chemical; ICS = Inhaled Glucocorticosteroid; LABA = Long-Acting Beta2-Agonist; LAMA = Long-Acting Muscarinic Antagonist; SABA = Short-Acting Beta2-Agonist; SAMA = Short-Acting Muscarinic Antagonist.

1 The national drug code of each database country will be used to identify medications without an individual ATC code.

Source: WHO Collaborating Centre for Drug Statistics Methodology. ATC/DDD Index 2013. Updated 20 December 2012. Available at: [website: whooc.no/atc_ddd_index/](http://website.whooc.no/atc_ddd_index/). Accessed 21 January 2013.

Proprietary confidential information © 2017 Boehringer Ingelheim International GmbH or one or more of its affiliated companies

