Annex Table 4:2 (con't) Anatomical Therapeutic Chemical codes for comedications

| Medication Description                                    | ATC Code  |
|---|---|
| Respiratory medications                            |   |
| Flunisolide   | R03BA03   |
| Betamethasone   | R03BA04   |
| Fluticasone   | R03BA05   |
| Triamcinolone   | R03BA06   |
| Mometasone  | R03BA07   |
| Ciclesonide   | R03BA08   |
| Fixed combinations of SABAs and SAMAs                     | ATC codes not available                                     |
| Fixed combinations of SABAs and ICSs                      | ATC codes not available                                     |
| Fixed combinations of LABAs and ICSs                      | ATC codes not available                                     |
| Systemic glucocorticosteroids                             | H02AB   |
| Systemic beta2-agonists                                   | R03CC   |
| Xanthines and adrenergics                                 | R03DA, R03DB  |
| Roflumilast   | R03DX07   |
| Nasal glucocorticosteroids                                | R01AD   |
| Omalizumab  | R03DX05   |
| Leukotriene receptor antagonists                          | R03DC   |
| Cromoglicic acid  | R03BC01   |
| Nedocromil  | R03BC03   |
| Methotrexate  | L04AX03   |
| Ciclosporin   | L04AD01   |
| Gold preparations   | M01CB   |
| Oxygen therapy  | V03AN01   |
| Nebuliser therapy   | ATC codes not available                                     |
| Cardiovascular medications                         | All codes listed below in section
Cardiovascular medications |
| Cardiac glycosides and antiarrhythmics, Classes I and III | C01A, C01B  |
| Vasodilators used in cardiac diseases                     | C01D  |
| Other cardiac preparations                                | C01B, C01C  |
| Diuretics   | C03   |
| Peripheral vasodilators                                   | C04   |

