The study period will start on the date of olodaterol launch in each country and will end on the latest date the data are available at the time of data extraction. Anticipated study periods for each data source at the time of data extraction and reporting milestones are shown in [Table 1](#).

Proprietary confidential information © 2017 Boehringer Ingelheim International GmbH or one or more of its affiliated companies

Table 1 Estimated study period in each study data source and reporting milestones

Event	PHARMO, the Netherlands	National Registries, Denmark	IMS RWE LPD, France
Olodaterol launch in country	March 2014	January 2014	October 2015
Data extraction for interim report	Q1 2017	Q1 2017	Q1 2017
Anticipated study period included in interim report ¹	March 2014 – Q4 2015	January 2014 – Q4 2015	October 2015 – Q4 2016
Interim report regulatory milestone	Q3 2017	Q3 2017	Q3 2017
Data extraction for final report	Q1 2018	Q1 2018	Q1 2018
Anticipated study period for final report	March 2014 – Q4 2016	January 2014 Q4 2016	October 2015 – Q4 2017
Final report regulatory milestone	Q3 2018	Q3 2018	Q3 2018

IMS = IMS Health Information Solutions; PHARMO = PHARMO Database Network; Q_n = the quarter of the calendar year; RWE LPD = Real-World Evidence Longitudinal Patient Database.

1. Study periods of observation are estimated based on the following lag times in each data source: PHARMO, approximately 6 to 18 months, Danish registries, approximately 6 to 12 months; IMS RWE LPD, 2 to 7 months.

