5.1 MAIN OUTCOMES

The main outcome of the study is the prevalence of off-label prescribing among new users of olodaterol. As a secondary outcome, the prevalence of off-label prescribing among new users of indacaterol will be assessed.

According to age and the presence of a recorded diagnosis of COPD and/or asthma, new users of olodaterol and new users of indacaterol will be classified into the following categories ([Table 4](#)):

- On-label prescribing: adults (aged ≥ 18 years at the index date) with a recorded diagnosis of COPD, with or without asthma
- Off-label prescribing:
 - Adults (aged ≥ 18 years at the index date) with a recorded diagnosis of asthma and without a recorded diagnosis of COPD, and
 - All children (aged < 18 years), irrespective of whether they have a recorded diagnosis of COPD (unlikely), asthma, or other respiratory disease
- Potential off-label prescribing: adults (aged ≥ 18 years) without a recorded diagnosis of COPD or asthma:
 - To further characterise these patients, recorded diagnosis of “other respiratory comorbidities” among these patients will be described (see conditions included in [Section 5.3.4](#)). The possibility of these patients having “probable COPD” will also be

Proprietary confidential information © 2017 Boehringer Ingelheim International GmbH or one or more of its affiliated companies

explored. Probable COPD will be defined by the presence of at least two prescriptions of long-acting beta2-agonist (LABA), long-acting muscarinic antagonist (LAMA), or inhaled glucocorticosteroid (ICS) (or combination) after the age of 40 years but not before (see lists of medications in [Annex Table 1-6](#)).

Table 4 Classification of patients according to age and indication of olodaterol and indacaterol

Recorded diagnosis ¹	Age	On-label prescribing: indication of COPD	Off-label prescribing	Potential off-label prescribing
COPD	≥18	Yes		
COPD and asthma	≥18	Yes		
Children, irrespective of any recorded diagnosis	<18		Yes	
Asthma (no COPD)	≥18		Yes	
No COPD, no asthma ²	≥18			Yes

COPD = Chronic Obstructive Pulmonary Disease.

- 1 Diagnosis recorded at any time before or on the index date and up to 30 days after the index date.
- 2 To further characterise adult patients with no COPD and no asthma, “potential COPD” and “other respiratory conditions” will be described among these patients.

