6. GENERAL ANALYSIS DEFINITIONS

6.1 EXPOSURE

The main study exposures of interest are olodaterol and indacaterol. New users of olodaterol and indacaterol will be identified at the first record of a prescription/dispensing for the relevant medication code specific to each database within the study period (see [Table 1](#) for study periods in each data source).

For these medications, the following characteristics will be described:

- *Daily dose at the index date* (µg): the dose prescribed by the physician at the index date, when available, or ascertained by the dispensed defined daily dose (DDD) and the estimation of the daily dose at index date. The estimated daily dose dispensed at the index date will be calculated using the recorded information on strength and quantity dispensed and the days of supply of the first prescription for olodaterol and indacaterol. Missing values for dose are expected and will be described.
- *Number of packages at the index date*: the number of packages prescribed by the physician, when available, or ascertained by the dispensed DDD. The estimated number of packages dispensed at the index date will be calculated using the recorded information on quantity dispensed and/or the days of supply of the first prescription for olodaterol and indacaterol. Missing values for dose are expected and will be described.

Information of interest to identify the drugs of interest and the daily dose and the number of packages at the index date is described in [Table 10](#).

Table 10 Information on olodaterol and indacaterol

Descriptor	Indacaterol	Olodaterol
Brand name	Onbrez Breezhaler (Hirobriz Breezhaler and Oslif Breezhaler in The Netherlands)	Striverdi Respimat
ATC	R03AC18	R03AC19
Formulation	Inhalation powder	Solution for inhalation
Presentation	Capsules	Cartridges
Strengths	150 mcg and 300 mcg	2.5 mcg
Package size	30 capsules	60 cartridges
DDD	150 mcg	5 mcg
Recommended dose	150 mcg once a day	2 puffs of 2.5 mcg once a day
Maximum dose	300 mcg once a day	5 mcg once a day

ATC = Anatomical Therapeutic Chemical; DDD = Defined Daily Dose.

Source: Onbrez Summary of Product Characteristics [\[R16-2634\]](#); Striverdi Summary of Product Characteristics [\[R16-2633\]](#); WHO Collaborating Centre for Drug Statistics Methodology. ATC/DDD Index 2015. Available at: https://www.whocc.no/atc_ddd_index/.

Proprietary confidential information © 2017 Boehringer Ingelheim International GmbH or one or more of its affiliated companies

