6.5 HANDLING OF MISSING DATA AND OUTLIERS

The extent of missing data will be evaluated and described. Due to the nature of this study, no imputation of missing data is planned. Missing values are expected in some sociodemographic variables depending on the definition used and in variables related to exposure characterisations such as strength or daily dose. Degree of missingness will depend on the database, and some data sources will have variables that are not available, such as oxygen therapy in PHARMO and hospitalisations in IMS RWE LPD. Diagnoses, prescriptions, and dispensings can be identified in the databases only if they are recorded. Thus, all patients with a certain diagnosis/dispensing in the database will be coded as having

Proprietary confidential information © 2017 Boehringer Ingelheim International GmbH or one or more of its affiliated companies

the respective condition/exposure to the respective drug. All others will be coded as not having the disease/not being exposed to the drug. Therefore, uncoded diagnoses/dispensings may result in misclassification and not in missing values.

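### SAP Annex Table 1-6 defines the inhaled LAMA, LABA, ICS and LABA/ICS classes by closed lists of single ATC codes under a December 2012 source line, and the list already omits olodaterol (R03AC19)

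*SAP*

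**What the plan says.** SAP Section 5.3.6 defines comedications by Annex Table 1-6. The source line of that annex reads "ATC/DDD Index 2013. Updated 20 December 2012", accessed in January 2013. The protocol's Annex Table 4:2 carries the same source line. Table 10 in SAP Section 6.1, which describes the study drugs, cites "ATC/DDD Index 2015".

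In Annex Table 1-6 the inhaled classes are listed substance by substance. The LAMA rows end at "Glycopyrronium bromide" (R03BB06) and the LABA/ICS rows at "Salmeterol and budesonide" (R03AK12). Most non-respiratory rows, and some respiratory ones, are ATC groups: C03, C07, J01, N06A, H02AB, R03CC.

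Four analyses draw on the annex:

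- the comedication tables (Section 7.2);
- the all-medication and respiratory dispensing counts (Table 7);
- the same-class rule that separates Mild from Moderate COPD (Section 5.3.3);
- 'probable COPD' in Section 5.1, which sends the reader to the annex with "see lists of medications in".

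Section 6.5 says of patients with no matching record: "All others will be coded as not having the disease/not being exposed to the drug". The row "Anticipated study period for final report" in SAP Table 1 runs from January 2014 (Denmark) to Q4 2017 (France).

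**The concern.** A group code takes in a new product as soon as that product is coded. A closed list does not. If a patient's LAMA or ICS has a code outside the list, the tables show no use and nothing in the output reveals the omission. That matters because describing baseline characteristics of new users is a primary objective, and because 'probable COPD' is how the report will interpret adults with neither a COPD nor an asthma diagnosis.

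The source line adds a traceability problem. One SAP cites two index years, and the comedication list was edited without its citation being changed. A reader cannot tell which version of the ATC index the analysis would use.

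**Working it through.** **1. The two annexes side by side.**

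| Class | Protocol Annex Table 4:2 | SAP Annex Table 1-6 | Catch-all row |
|---|---|---|---|
| LAMA | R03BB04 to 06 (3 codes) | same | none |
| LABA | R03AC12, R03AC13 (2 codes) | same | none |
| ICS | R03BA01 to 08 (8 codes) | same | none |
| LABA/ICS | one row, "Fixed combinations of LABAs and ICSs", with no ATC code | R03AK06 to 12 (7 codes), plus the uncoded row | national drug codes |

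The SAP list was therefore revised for LABA/ICS but not for LAMA, LABA or ICS. The national-drug-code footnote applies only to drugs that have no ATC code of their own, so it does not rescue a LAMA or ICS that has received one.

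**2. A gap visible in the documents.** Across the SABA and LABA rows, the annex lists R03AC02 to R03AC18: 15 codes under SABA (including indacaterol, R03AC18) and 2 under LABA. Table 10 gives olodaterol as R03AC19, which is not in the annex. Table 7 defines respiratory dispensings by the annex, and its footnote says indacaterol is counted in the olodaterol cohort and the reverse. As the list stands, prior indacaterol is counted in the olodaterol cohort, but prior olodaterol is not counted in the indacaterol cohort. Section 6.3 lets one patient enter both groups, so the case can arise.

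**3. Age of the cited index.** Months = days since 20 December 2012 / 30.4375, using the first day of each starting month and 31 December of the final year in Table 1:

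- Netherlands, 1 March 2014 to 31 December 2016: 436 / 30.4375 = 14.3, to 1472 / 30.4375 = 48.4 months.
- Denmark, 1 January 2014 to 31 December 2016: 377 / 30.4375 = 12.4, to 48.4 months.
- France, 1 October 2015 to 31 December 2017: 1015 / 30.4375 = 33.3, to 1837 / 30.4375 = 60.4 months.

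**4. What an omission would do.** The documents give no share of users on unlisted products. Let p be true class use and f the share of those users whose only product in the class is unlisted; observed use is p x (1 - f). Purely as an assumption, take f from 0 to 30%:

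| f | 0% | 5% | 10% | 20% | 30% |
|---|---|---|---|---|---|
| Observed if p = 40% | 40% | 38% | 36% | 32% | 28% |
| Observed if p = 20% | 20% | 19% | 18% | 16% | 14% |

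**5. Where it reaches.** The comedication tables and dispensing counts are affected directly. 'Probable COPD' needs two prescriptions of any listed LABA, LAMA, ICS or combination after age 40, so a patient loses the label only if fewer than two listed prescriptions remain. Its condition of no such prescription before 40 could occasionally work the other way. For severity, Section 5.3.3 pools SAMA, LAMA, SABA, LABA and SABA/SAMA into one bronchodilator class. A missed product moves a patient from Moderate to Mild only if no two listed dispensings of any one class remain within six months. The main classification in Sections 5.1 and 7.5.1 uses age and diagnoses only.

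**The case against.** The strongest reply is that an old citation does not prove an old list. The R03AK codes were added under an unchanged source line, so someone reviewed the annex after the protocol. That stands: a reader might infer that coding stopped in December 2012, and the documents do not support this. What remains is that the version in use cannot be traced and that the LAMA, LABA and ICS rows did not change.

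Second, apart from olodaterol the documents name no product coded after the cited index. This also stands. A loss of other LAMA or ICS products is a risk built into the closed lists and has not been demonstrated. For LABA/ICS, the uncoded row may catch some combinations.

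Third, Section 6.5 is about events that are not recorded or coded, and does not mention a recorded drug missing from an annex. That is a fair reading, but the point does not depend on Section 6.5. Sections 5.3.2 and 5.3.6 define these variables by the annex, so an unlisted code is outside the definition.

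Fourth, SAP Section 9.2 holds database-specific definitions and is not in the text available for this review. It may extend the codes. No visible section promises a refresh, whereas Section 5.3.3 does announce source-specific lists for antibiotics and systemic glucocorticosteroids.

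**Conclusion.** The point holds in a limited form. The inhaled classes rest on closed code lists with an outdated and inconsistent citation. One code given elsewhere in the SAP, R03AC19, is missing where the Table 7 footnote needs it, and any other later-coded single-agent LAMA or ICS would be missed by the same mechanism. The possible effect is an undercount in the comedication tables, the dispensing counts and 'probable COPD'. The effect on Mild versus Moderate severity is limited and concerns the Netherlands and Denmark only, because severity is not described in France.

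A reader might go further and infer an error that grows from 2014 to 2017 and imitates a time trend or a French difference. The documents do not support that. The gap to the cited index does widen, from about 12 to 60 months, but no figure links it to lost dispensings. Only France reaches 2017, and its medication codes are mapped from another system. SAP Section 7.2 does not tabulate comedications by calendar year, although protocol Section 9.7.4 planned that stratification. Nor does the point touch the primary outcome: the on-label, off-label and potential off-label classes do not use this list.

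The size, any growth over time and any country difference cannot be computed from the documents. The percentages in the working illustrate an assumed share and are not estimates. The conclusion also assumes that Section 9.2 does not already extend the codes.

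**What to change.** - Add R03AC19 to the LABA rows of Annex Table 1-6.
- Define the inhaled classes at ATC group level: R03BB except the listed SAMAs (R03BB01, R03BB02) for LAMA, R03BA for ICS, and the LABA/ICS codes within R03AK. Name any substance that is excluded. For example, both annexes skip R03BB03, which the group rule would bring in, so the annex should say whether it counts.
- Refresh the list from the ATC index in force at each extraction (Q1 2017 and Q1 2018) and record the version used.
- Apply the same list to Table 7, 'probable COPD', severity and the comedication tables.
- Correct the source line so that it agrees with Table 10.

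The cost is annex wording, a code-list rerun at each extraction and a check for non-target products brought in by the group codes. No new data are needed.

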Annex Table 1-7 Database-specific codes for nebulisers in PHARMO

Devices	code
RESPIFLO VERNEVEL ADAPTER	14057816
VERNEVELAAR	14684217
MEDICIJN VERNEVELSET KENDALL MET AER MASKER KIND	14824256
MEDICIJN VERNEVELSET KENDALL MET AER MASKER VOLWAS	14824264
MONDSTUK VERNEVELAAR KENDALL LOS	14825678
MEDICIJN VERNEVELAAR KENDALL LOS	14825686
MEDICIJN VERNEVELSET KENDALL MET MONDSTUK	14825694
RESPIFLO CUP VOOR UN VERNEVELAAR 145ML	14826836
HUDSON ISONEB VERNEVELAAR	15136620
OMRON COMP AIR COMPRESSORVERNEVELAAR	15214508
OMRON COMP AIR ELITE COMPRESSORVERNEVELAAR	15214532
OMRON COMP AIR PRO COMPRESSORVERNEVELAAR	15214540
PARI EFLOW OPBERGZAK TBV VERNEVELAAR	15502155
PARI EFLOW VERBINDINGSKABEL NAAR VERNEVELAAR	15502198
PARI EFLOW VERNEVELSET INCLUSIEF MESH	15502201
PARI SINUS VERNEVELAAR COMPLEET	15502309
PARI TURBOBOY N MEDICATIE VERNEVELAAR COMPLEET	15502333
PARI LC PLUS VERNEVELAAR	15559025
PARI LC SPRINT VERNEVELAAR	15559033
OMRON COMP AIR COMPRESSORVERN COMPACT GEEL KIND	15910253
OMRON COMP AIR COMPRESSORVERNEVELAAR COMPACT WIT	15910261
VERNEVELSET INTERSURGICAL INCL FILTER Z FLOWMETER	16135067
CIRRUS 2 VERNEVELAAR	16135091
CIRRUS 2 VERNEVELAAR + KINDERMASKER + SLANG	16135105
CIRRUS 2 VERNEVELAAR + MONDSTUK + SLANG	16135113
VERNEVELMASKER INTERSURGICAL ECO KIND	16135121
T-STUK INTERSURGICAL MET VEER VOOR VERNEVELING	16135199

Proprietary confidential information © 2017 Boehringer Ingelheim International GmbH or one or more of its affiliated companies

